### 1. INTRODUCTION

The purpose of this SAP is to describe the planned analyses to be included in the clinical study report (CSR) for Study 218079 (ANCHOR-2). Details of the planned final analyses are provided.

The pre-specified pooled analysis across studies 218079 (this study: ANCHOR-2) and 217095 (replicate study: ANCHOR-1) will be described in a separate analysis plan.

### 1.1. Objectives, Estimands and Endpoints

### 1.1.1. Objectives and Endpoints

Objectives	Endpoints
Primary	
To evaluate the efficacy of depemokimab 100mg SC + SoC compared to placebo + SoC at Week 52 in participants with a diagnosis of CRSwNP	
 
Co-primary endpoints:
 
a) Change from baseline in total endoscopic NP score at Week 52 (centrally read)
 
b) Change from baseline in mean nasal obstruction score (verbal response scale [VRS]) from Week 49 through to Week 52
 

Secondary	
To evaluate the efficacy of depemokimab 100 mg SC + SoC compared to placebo + SoC at Week 52 in terms of symptom scores for rhinorrhoea (runny nose) and loss of smell	
 
Change from baseline in mean symptom score for rhinorrhoea (runny nose) (VRS) from Week 49 through to Week 52
 
Change from baseline in mean symptom score for loss of smell (VRS) from Week 49 through to Week 52
 

To evaluate the efficacy of depemokimab 100 mg SC + SoC compared to placebo + SoC at Week 52 in terms of the Lund Mackay CT score	Change from baseline in Lund Mackay CT score at Week 52
To evaluate the impact on quality of life of depemokimab 100 mg SC + SoC compared to placebo + SoC at Week 52 in patients with a diagnosis of CRSwNP	Change from baseline in SNOT-22 total score at Week 52

Objectives	Endpoints
To evaluate the efficacy of depemokimab 100 mg SC + SoC compared to placebo + SoC prior to	Change from baseline in mean nasal obstruction score (VRS) from Week 21 through to Week 24
Week 26 in participants with a diagnosis of CRSwNP	
 
Change from baseline in total endoscopic NP score at Week 26
 

Other	
To evaluate the efficacy of depemokimab 100 mg SC + SoC compared to placebo + SoC on	Change from baseline in mean overall symptom (VAS) score from Week 49 through to Week 52
individual NP symptoms	Achieving a one point or greater decrease from baseline in NP Score at Week 52 without first having nasal surgery (actual) or disease-modulating medication for CRSwNP
	• Change from baseline in mean individual symptom (VRS) score for facial pain from Week 49 through to Week 52
	• Change from baseline in mean individual symptom (VRS) score for mucus in throat from Week 49 through to Week 52
To evaluate the efficacy of depemokimab 100 mg SC + SoC compared to placebo + SoC on composite symptom endpoints	Change from baseline in the mean nasal polyps symptoms composite score (combining VRS scores for nasal obstruction, rhinorrhoea (runny nose), loss of smell, and mucus in throat) from Week 49 through to Week 52
	• Change from baseline in mean CRS symptoms and facial pain composite score (combining VRS scores for nasal obstruction, rhinorrhoea (runny nose), loss of smell, and facial pain) from Week 49 through to Week 52
	Achieving a meaningful decrease from baseline in their mean individual symptoms VRS and composite VRS from Week 49 through to Week 52 without first having nasal surgery (actual) or diseasemodulating medication for CRSwNP.
To evaluate the efficacy of depemokimab 100 mg SC + SoC	• Achieving an 8.9 point or greater decrease from baseline in SNOT-22 total score at

Objectives		Endpoints
compared to placebo + SoC on health-related quality of life		Week 52 without first having nasal surgery (actual) or disease-modulating medication for CRSwNP
		Achieving a 28 point or greater decrease from baseline in SNOT-22 total score at Week 52 without first having nasal surgery (actual) or disease-modulating medication for CRSwNP
		Change from baseline in SF-36 Mental Component Summary (MCS) score, Physical Component Summary (PCS) score and eight domains at Week 52
	•	Change from baseline in WPAI-GH scores at Week 52
Safety		
To evaluate the safety and tolerability of depemokimab		Incidence of AEs/ Serious adverse events (SAEs)
100 mg SC + SoC every 26 weeks, compared to placebo + SoC in patients with a diagnosis of CRSwNP		Change from baseline in vital signs (heart rate, systolic and diastolic blood pressure, body temperature) at discrete timepoints during the 52-week period
		Change from baseline in ECG values at discrete timepoints during the 52-week period
		Change from baseline in laboratory parameters (including haematological and clinical chemistry parameters) and hepatobiliary laboratory abnormalities at discrete timepoints during the 52-week period
		Incidence of immunogenicity as measured by the presence of ADA and neutralising antibodies (NAb) to depemokimab
Pharmacokinetics and Pharmacody	nami	cs
To evaluate the pharmacokinetics and pharmacodynamics of depemokimab 100 mg SC + SoC in		Depemokimab plasma concentration at measured timepoints during the 52-week period

Objectives	Endpoints
participants with a diagnosis of CRSwNP	Ratio to baseline in absolute blood eosinophil count at measured timepoints during the 52-week period.

### 1.1.2. Primary Estimands

The primary estimands are defined as follows:

**Treatment Comparison:** depemokimab 100 mg SC + SoC compared to placebo + SoC

**Population:** Participants with a diagnosis of CRSwNP

### Co-primary variables/endpoints:

- Change from baseline in total endoscopic NP score at Week 52 (centrally read)
- Change from baseline in mean nasal obstruction score (verbal response scale [VRS]) from Week 49 through to Week 52

**Summary measure**: Difference in means between treatment groups - depemokimab 100 mg SC + SoC versus placebo + SoC

#### Main Intercurrent events (ICE) anticipated:

- Surgery, which includes any procedure involving instruments resulting in incision and removal of tissue from the nasal cavity (e.g. polypectomy and endoscopic sinus surgery (ESS)) to be handled using a composite strategy by incorporating occurrence of the event into the definition of the endpoint. Specifically, participants who undergo surgery will be assigned the worst possible value of the relevant score for all assessments following surgery i.e. the worst value that it is possible to select on the given scale).
- Premature discontinuation of study treatment to be handled using a treatment policy strategy
- Initiation of a medication that may modulate the disease course of CRSwNP by reduction of blood eosinophils or type II inflammation to be handled using a composite strategy by incorporating the occurrence of the event into the definition of the endpoint. Medications that may modulate the disease course to be selected either based on published evidence or mechanism of action, and to include the initiation of some biologics, chronic SCS and INCS. Specifically, participants who start a medication that may modulate the disease course of CRSwNP will be assigned the worst possible value of the relevant score for all assessments following the start of the medication (i.e., the worst value that is possible to select on the given scale).
  - All other changes in background medication or start of a prohibited medication to be handled using a treatment policy strategy
- COVID-19 related events to be handled using a treatment policy strategy

• Course(s) of systemic corticosteroid (CS) for CRSwNP any reason – to be handled using a treatment policy strategy

**Supplementary estimand strategy for co-primary endpoints:** In addition, the intercurrent event for all changes in background medication or start of a medication that may modulate the disease course of CRSwNP to be handled under the treatment policy strategy will be considered as a supplementary estimand to the primary estimand.

### 1.1.3. Secondary Estimands

The secondary estimands are defined as follows:

Treatment Comparison: As for primary estimand

Population: As for primary estimand

[figure not shown]
#### Variables/endpoints:

[figure not shown]
- Change from baseline in mean symptom score for rhinorrhoea (runny nose) (VRS) from Week 49 through to Week 52
- Change from baseline in mean symptom score for loss of smell (VRS) from Week 49 through to Week 52
- Change from baseline in Lund Mackay CT score at Week 52
- Change from baseline in SNOT-22 total score at Week 52
- Change from baseline in mean nasal obstruction score (VRS) from Week 21 through to Week 24
- Change from baseline in total endoscopic NP score at Week 26

[figure not shown]
**Summary measure**: As for primary estimand

Main Intercurrent events (ICE) anticipated: As for primary estimand

# 1.2. Study Design

### 2. STATISTICAL HYPOTHESES

The study is designed to test the inequality of depemokimab 100 mg SC vs. placebo (both in addition to SoC) in both co-primary endpoints of total endoscopic NP score at Week 52 and mean nasal obstruction VRS symptom score from Week 49 through to Week 52. Each co-primary endpoint will be tested at the two-sided 5% alpha level, both tests are required to be significant to achieve the primary objective of this study.

Demonstration of efficacy for each of these tests will be based on a hypothesis testing approach, whereby the null hypothesis is that there is no difference between treatment groups for the endpoint of interest and the alternative hypothesis is that there is a difference between treatment groups.

[figure not shown]
# 2.1. Multiplicity Adjustment

The hypotheses to be tested are structured as shown in Figure 1. The co-primary endpoints will be tested first and if these comparisons are both significant at the 2-sided 5% level, testing will continue for the secondary endpoints within the study according to the testing procedure detailed in Figure 1. Testing of secondary endpoints will be carried out in a hierarchical manner, dependent on statistical significance having been achieved for the previous endpoint in the hierarchy. Other pairwise comparisons will be performed

but are not part of the multiple testing strategy. Analyses of other efficacy measures are nested under the secondary efficacy measures and no multiplicity adjustment is planned for these other efficacy endpoints. The analyses for these other efficacy endpoints and some of the earlier time points for some of the co-primary and secondary endpoints are not adjusted for multiplicity and so nominal significance will be evaluated in a descriptive manner with these analyses using a 5% reference level.

A pre-specified pooled analysis of data from the ANCHOR-1 and ANCHOR-2 studies is planned for the secondary endpoints of time to first nasal surgery (actual or entry on waiting list) or disease-modulating medication for CRSwNP, time to first nasal surgery (actual) or disease-modulating medication for CRSwNP, proportion of participants requiring at least 1 course of systemic corticosteroids or disease-modulating medication for CRSwNP or nasal surgery (actual), and change from baseline in ACQ-5 score in participants with an ACQ score of >0.75 at baseline. This pooled analysis will be carried out after statistical significance is achieved for both co-primary endpoints within both studies. The closed-testing manner for the pre-specified pooled hierarchy is described further in the pooled SAP.

Figure 1 Conceptualization of Statistical Testing Strategy Across Studies ANCHOR-1 and ANCHOR-2

Note: Endpoint names in Figure 1 are abbreviated. Refer to Section 1.1 for full nomenclature of endpoints.

# 3. ANALYSIS SETS

Analysis Set	Definition / Criteria	Analyses Evaluated
Screened	All participants screened and for whom a record exists on the study database	• Study population
Screened- China	All participants screened and for whom a record exists on the study database from China	• Study population
Screened- Japan	All participants screened and for whom a record exists on the study database from Japan	Study population
Enrolled	Nly	Study population
Randomized	All randomized participants	

Study population

Full Analysis Set (FAS)	All randomized participants who take at least 1 dose of study treatment excluding participants from sites 255403 and 255387. Participants will be analyzed according to the treatment they are allocated at randomization.	

Study population

Efficacy

FAS-China	All participants in the FAS population who are enrolled from China	

Study population

Efficacy

FAS-Japan	All participants in the FAS population who are enrolled from Japan and are of Japanese heritage only	

Study population

Efficacy

FAS-Modified	All participants in the FAS population plus randomised participants from sites 255403 and 255387 who receive at least one dose of study treatment.	

Study population

Efficacy

Safety	All randomized participants who take at least 1 dose of study treatment excluding participants from sites 255403 and 255387. Participants will be analyzed according to the treatment they are allocated at randomization, unless the participant receives a different treatment to randomized active treatment at all protocol-defined administrations at which study medication was received, in which case the participant will be analyzed according to the actual treatment they received.	Safety
Safety-China	All participants in the Safety population who are enrolled from China	Safety
Safety-Japan	All participants in the Safety population who are enrolled from Japan and are of Japanese heritage only	Safety
Safety- Modified	All randomized participants who take at least 1 dose of study treatment excluding participants from sites 255403 and 255387. Participants will be analyzed according to the treatment they are allocated at randomization, unless the participant receives a different treatment to randomized active treatment at all protocol-defined administrations at which study medication was received, in which case the participant	Safety

Analysis Set	Definition / Criteria	Analyses Evaluated
	will be analyzed according to the actual treatment they received.	
PK	All participants in the FAS population for whom at least one pharmacokinetic sample was obtained, analyzed and was measurable, including imputed values that were below the limit of quantification. Participants will be analyzed according to the treatment they received.	• PK
PK-China	All participants in the PK population who are enrolled from China	• PK

Note: The Japan Ministry of Health, Labour and Welfare (MHLW) confirmed GCP violations in several studies involving Medipharma, a Japanese Site Management Organisation (SMO). Medipharma provided site management services to sites 255403 and 255387 in ANCHOR-2.

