9.2. Analysis Sets

For the purposes of analysis, the following analysis sets are defined:

Participant Analysis Set	Description
Screened	All participants screened and for whom a record exists on the study database.
Screened-China	All participants screened and for whom a record exists on the study database from China.
Screened-Japan	All participants screened and for whom a record exists on the study database from Japan.
Randomised	All randomised participants
Full Analysis Set (FAS)	All randomised participants who take at least 1 dose of study treatment excluding participants from sites 255403 and 255387 ^a . Participants will be analysed according to the treatment they are allocated at randomisation.
FAS-China	All participants in the FAS population who are enrolled from China.
FAS-Japan	All participants in the FAS population who are enrolled from Japan and are of Japanese heritage only.
FAS-Modified	All participants in the FAS population plus randomised participants from sites 255403 and 255387 ^a who receive at least one dose of study treatment.
Safety	All randomised participants who take at least 1 dose of study treatment excluding participants from sites 255403 and 255387a. Participants will be analysed according to the treatment they are allocated at randomisation, unless the participant receives a different treatment to randomized active treatment at all protocol-defined administrations at which study medication was received, in which case the participant will be analysed according to the actual treatment they received.
Safety-China	All participants in the Safety population who are enrolled from China.
Safety-Japan	All participants in the Safety population who are enrolled from Japan and are of Japanese heritage only.
Safety-Modified	All participants in the safety population plus randomised participants from sites 255403 and 255387a who receive at least 1 dose of study treatment Participants will be analysed according to the treatment they are allocated at randomisation, unless the participant receives a different treatment to randomized active treatment at all protocol-defined administrations at which study medication was received, in which case the participant will be analysed according to the actual treatment they received.

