#### 4. STATISTICAL ANALYSES

#### 4.1. General Considerations

### 4.1.1. General Methodology

Unless otherwise stated, the Safety Analysis Set be used for safety displays and the Full Analysis Set (FAS) will be used for all other displays. FAS-Modified and Safety-Modified analysis sets will be used for a selected number of displays as sensitivity analyses. FAS-China, FAS-Japan, Safety-China and Safety-Japan will be used for China and Japan specific outputs respectively. The Programming Specification document will provide more details.

Unless otherwise stated, all intercurrent events for primary, secondary, or other endpoints will be handled under the primary estimand strategy.

This SAP specifies the analytical approaches for the global submission requirements, unless otherwise specified. Further analytical considerations may be made for the regional displays (i.e. model convergence considerations) where appropriate.

The randomization is stratified based on occurrence of previous surgery for nasal polyps and unless otherwise stated, this variable will be included as a covariate in the statistical models. In the case of an incorrect stratification at the time of randomization, the actual stratum will be used rather than the randomized stratum.

Confidence intervals will use 95% confidence levels unless otherwise specified.

Unless otherwise specified, continuous data will be summarized using descriptive statistics: n, mean, standard deviation (std), median, minimum and maximum. Categorical data will be summarized as the number and percentage of participants in each category.

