# 4.5. Safety Analyses

The safety analyses will be based on the Safety Analysis Set, unless otherwise specified.

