# 4.12. Changes to Protocol Defined Analyses

There were no changes or deviations to the originally planned statistical analysis specified in the protocol.

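### The SAP's Safety-Modified set repeats the Safety definition, so the planned safety sensitivity analysis tests nothing and the two excluded sites' dosed participants are in no safety set

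*SAP*

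**What the plan says.** Two sites, 255403 and 255387, were served by a site management organisation for which the Japanese health ministry confirmed GCP violations in several studies. The plan removes them from the main analysis sets and creates modified sets to bring them back.

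- **Protocol Section 9.2, Safety-Modified:** "All participants in the safety population plus randomised participants from sites 255403 and 255387a who receive at least 1 dose of study treatment". (The letter after the second site number is a footnote marker.)
- **SAP Section 3, Safety and Safety-Modified:** both rows open with "All randomized participants who take at least 1 dose of study treatment excluding participants from sites 255403 and 255387" and then give the same treatment-assignment rule.
- **SAP Section 3, FAS-Modified:** "All participants in the FAS population plus randomised participants from sites 255403 and 255387 who receive at least one dose of study treatment".
- **SAP Section 4.1.1:** "FAS-Modified and Safety-Modified analysis sets will be used for a selected number of displays as sensitivity analyses".
- **SAP Section 4.5:** "The safety analyses will be based on the Safety Analysis Set, unless otherwise specified".
- **SAP Section 4.12:** "There were no changes or deviations to the originally planned statistical analysis specified in the protocol".

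**The concern.** A modified safety set is useful only if it contains people the main set leaves out. Here the main Safety set omits participants who were randomised and dosed. That makes the add-back analysis the one planned safety summary that could show whether the omission changes the adverse-event picture.

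If the SAP row is programmed literally, the sensitivity displays reproduce the main ones. A reader who does not check the definitions could take the agreement as evidence of robustness when nothing was compared. Adverse events and serious adverse events from dosed participants at the two sites would also enter no safety summary based on an SAP analysis set. The efficacy and safety modified sets, meant to be parallel, would cover different people.

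**Working it through.** The documents give no figure to reproduce. The check is a comparison of set definitions.

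**Notation.** Let D be all randomised participants with at least one dose, and X the members of D at sites 255403 and 255387. Let k be the size of X, which the documents do not state.

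| Set | Source | Membership |
|---|---|---|
| Safety | Protocol 9.2 and SAP 3 | D minus X |
| Safety-Modified | Protocol 9.2 | (D minus X) plus X = D |
| Safety-Modified | SAP 3 | D minus X |
| FAS-Modified | Protocol 9.2 and SAP 3 | (D minus X) plus X = D |

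**Step 1: what the sensitivity analysis adds.** Under the protocol, Safety-Modified less Safety is D less (D minus X) = X, which is k participants. Under the SAP it is (D minus X) less (D minus X), which is empty: 0 participants whatever k is. The treatment-assignment rule is also the same in both SAP rows, so the groups match as well as the membership. Any count, percentage or risk difference from the two sets must be identical.

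**Step 2: whether another safety set covers X.** The SAP's safety sets are Safety, Safety-China, Safety-Japan and Safety-Modified. The China and Japan sets are subsets of Safety, so they cannot contain any of X. As written, neither can Safety-Modified. X is therefore in no SAP safety set.

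**Step 3: whether X is absent everywhere.** It is not. X belongs to the Randomized set and to FAS-Modified, which SAP Sections 4.2.2 and 4.3.2 use for additional co-primary and secondary analyses. The gap is confined to safety. The two modified sets then differ by k participants, where the protocol gives both the same membership.

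**Step 4: whether the difference was intended.** Nothing suggests so. SAP Amendment 01 is based on Protocol Amendment 5, the current version. Its version history lists Safety-Modified as a set added alongside FAS-Modified, and Section 4.12 declares no change. The protocol's amendment history, read only for intent, says the modified sets were added to include these participants.

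**Step 5: whether it is an extraction fault.** The row is complete and grammatical, and it runs on correctly into the continuation of the table. The neighbouring FAS-Modified row reads properly.

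**Scale.** Against the planned 250 randomised participants, each person in X is 1/250 = 0.4%. Nothing further can be said without k.

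**The case against.** The strongest reply is that this is a transcription slip with an obvious intended meaning. The protocol has the right definition, the FAS-Modified row shows the pattern, and a set identical to Safety could not serve as a sensitivity set. SAP Section 6.1.1 also plans a table of the number of participants in each analysis set. If k is above zero, that table would show Safety-Modified equal to Safety while FAS-Modified exceeded FAS, so the error should be noticed. The Programming Specification, to which SAP Section 4.1.1 defers for detail, may already be correct.

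Safety oversight is not affected either. Collection and reporting of serious adverse events and the independent data monitoring committee's review are not described as leaving out these sites. Excluding them from the main Safety set is the protocol's own decision. What is lost is a selected number of secondary displays.

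Most of this stands, and it limits the point to sensitivity displays and to safety sets. It does not remove the error. The SAP states the rule, and followed literally the rule gives the wrong set. The Programming Specification is not among the documents and cannot be relied on to override an approved SAP. A count table that might expose the mistake once outputs exist is a weaker safeguard than a correct definition.

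**Conclusion.** The concern holds. As written, SAP Safety-Modified equals SAP Safety, contrary to Protocol Section 9.2. The planned safety sensitivity contrast is exactly zero by construction, and all k dosed participants at the two sites fall outside every SAP safety set.

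The conclusion rests on the SAP text alone and assumes only that k is above zero, which the creation of the modified sets implies. Whether the safety conclusions would change cannot be judged, because k and the events at those sites are not given. No alpha, power, sample size, co-primary result or main safety table is affected. A copying error is the likely cause, but the row must be corrected because it determines which participants are counted.

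**What to change.** Replace the SAP Section 3 Safety-Modified row with the protocol definition: everyone in the Safety set, together with randomised participants from sites 255403 and 255387 who received at least one dose. Keep the existing treatment-assignment rule. Then check that the Programming Specification and any dataset population flags follow the corrected row, and that the analysis-set count table shows Safety-Modified exceeding Safety by the number of dosed participants at the two sites.

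The cost is one table row and a consistency check. The displays are already planned, and no new data or analyses are needed.
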